20 STOPPING RULES

The following events will result in the study stopping:

- If two subjects commit suicide
- If three subjects attempt suicide
- If ≥ 2 serious adverse events (SAEs) occur that are device-related, as determined by investigators, the IRB, the FDA, or the Clinical Events Committee (CEC)

If any of the stopping rules are reached, enrollment will be paused and the FDA will be notified in a supplement to enable review of the information.

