7 SCHEDULE OF PROCEDURES

Table 1. Schedule of Procedures. Activities in blue cells are performed by trained graduate researchers supervised by a trained psychiatrist, and red cells are to be completed by the participant.

	Pre-Treatme nt		E	Blinded Pha	ise		Open-La Phas	abel e	Early termination ⁸
Activity	Week -3 to -1 (± 3 days)	Week 0	Week 1 (± 3 days)	Week 4 (± 3 days)	Week 7 (± 3 days)	Week 10 (± 3 days) Final blinded visit ¹	Week 10 (± 3 days) Open Label Start	Wee k 20 (± 3 days)	Week 1-20
Informed Consent	х								
Screening and baseline Video Call	х								
Diagnostic Assessment for MDD	X٩								
Intervention Kit Shipped to subject	X ⁵								
Randomization ⁶		Х							
Technical onboarding		х							
Initial Visit		Х							
Video call	Х	Х	Х	Х	Х	Х		Х	Х
MINI	Х								
HDRS-17	X		X	Х	X	X		X	X
MADRS	Х		Х	Х	Х	Х		X	Х
MADRS-s	X	X ⁴	X	X	X	X		X	Х
C-SSRS	X		X X	X X	X X	X		X	X X
YMRS	X X		X	X	X	X X		X	X
HAM-A	X					X		X X	X
EQ-5D-3L RAVLT	X					X		X	X
SDMT	~	X ²				 X ²		Λ X ²	^
TAQ	X	~				X		X	Х
AEQ						X		X	X
Healthcare Visit Survey ³						X		X	X
FLOW FL-100 use ⁷		х	х	х	х	х	х	Х	
Record/Review Concomitant Medications	х	х	х	х	х	х		х	х
Record/Review Adverse Events		Х	Х	Х	Х	Х		Х	Х

CA-127-T1, v3.0 Flow Neuroscience AB, FL001 CONFIDENTIAL Page **19** of **69**

¹ The week 10 visit includes the study Primary end-point. This will be the final blinded visit and will be the start of the open label phase of the study. Participants in the Sham arm will be informed of their assignment and will restart with active stimulation for 10 weeks; participants in the Flow FL-100 arm will be allowed to continue maintenance treatment for 10 more weeks at 3 sessions per week. The unblinding will occur after the primary end-point data has been recorded. ² Optional

³ Participants will be surveyed about the number of times he/she has sought healthcare due to depression during the previous 10 weeks.

⁴ Participants will be required to answer the nine questions of the MADRS-s form in the app to start the first stimulation session during the technical onboarding.

⁵ Participants will be required to start treatment within 24 days from completing the baseline surveys.

⁶ Completed after eligibility is confirmed by the investigator; when the participant signs up with their email in the trial app they will automatically be randomized to the sham or active treatment arm (with 50% probability).

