11.1 STUDY DURATION

The study is expected to take approximately 10 months from first participant enrolled to the last open-label visit.

- 5 months enrollment period (estimation)
- 5 months treatment and open-label

The follow-up period during the clinical investigation shall permit the demonstration of performance over a period, sufficient to represent a realistic test of the performance of the investigational device and allow any risks associated with adverse device effects over that period to be identified and assessed.

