12.4 Study Enrollment Procedures

All participants with MDD will be considered for screening into the study. Participants expressing an interest in participation will proceed with the consent process as per section 13.1 Informed Consent. A participant is not considered officially enrolled in the study until after signing the study consent form.

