12.4.1 PARTICIPANT ENROLLMENT

Participants who consent to participate shall be assigned a unique Participant Identification Number to de-identify their information. This Participant Identification Number will be captured in the Curebase platform and used to identify them on all source documents and eCRFs thereafter.

A record of all screened participants will be maintained in the Curebase platform. The date of screening, results of screening (included or not) and, if not eligible, the primary reason for excluding the participant, enrollment status (enrolled or not) and, if not enrolled, the primary reason will be recorded.

Please note, for purposes of the study a participant is considered enrolled at informed consent.

NOTE: If a participant does not meet the eligibility criteria during their initial screening, the participant cannot be re-evaluated for entry into the study later.

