12.6 PARTICIPANT TREATMENT ASSIGNMENT

During the technical onboarding session at Week 0, the participant will receive the link to the app and a code to access the app. The participant will download the app and sign up in the app with their email, password, and app access code. When the participant creates their account in the trial app they will automatically be randomized to the sham or active treatment arm (with 50% probability). Block randomization is used with randomly permuted block sizes of 4 and 6. This is done by the trial server and stored in its dedicated database. No one who is working with the trial will have access to the raw data until it has ended.

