13.9 STUDY COMPLETION/DISCONTINUATION

The Primary Endpoints will be evaluated at 10 weeks. Participants will complete study participation at 10 weeks unless consented and enrolled in an additional 10-week open-label portion of the study. Participants enrolled in the open-label phase will complete the trial after 20-weeks.

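### Section 20 says the listed events stop the study, but the only actions it fixes are a pause of enrolment (defined as consent) and FDA notification, so randomisation and first treatment of people already consented are not clearly held

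*Protocol*

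**What the plan says.** Section 20 opens with the consequence: "The following events will result in the study stopping". The triggers are two suicides, three suicide attempts, or at least two serious adverse events judged device-related. It closes with the action: "If any of the stopping rules are reached, enrollment will be paused and the FDA will be notified in a supplement", so that the information can be reviewed. No other action is named.

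The protocol defines enrolment twice, both times as consent. Section 12.4: "A participant is not considered officially enrolled in the study until after signing the study consent form". Section 12.4.1: "Please note, for purposes of the study a participant is considered enrolled at informed consent".

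The screening call and kit shipment follow consent (13.1). Randomisation takes place at Week 0 (12.6): "When the participant creates their account in the trial app they will automatically be randomized". A footnote to the Schedule of Procedures limits the wait before the first session: "Participants will be required to start treatment within 24 days from completing the baseline surveys".

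The open-label phase is described in two ways. Section 13.9 says participants finish at Week 10 "unless consented and enrolled in an additional 10-week open-label portion of the study", whereas 11.4 and 13.4 simply offer further treatment at Week 10.

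Section 16.1 obliges the sponsor to suspend the investigation if an unacceptable risk is suspected, or when the ethics committee or a regulator so instructs. Section 16.2 governs resumption and requires ethics committee concurrence. Section 20 refers to neither.

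**The concern.** The triggers are fixed counts, so that nobody has to judge case by case whether the trial should halt. The response should be equally definite. Instead, the section announces that the study stops and then names an action that, on the protocol's own definition, reaches only people who have not yet signed consent. Staff told that enrolment is paused could reasonably conclude that those already consented and holding a kit may go ahead.

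At stake is whether new people begin home stimulation while suicides, suicide attempts or device-related serious events are under review. The individual safeguards do not answer this. Sections 15.2 and 15.4 withdraw the affected participant and disable that person's device, but they do nothing for others waiting to start. Section 20 also says nothing about stimulation already under way, although section 9.2.1 notes that devices can be disabled remotely.

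**Working it through.** No figure in the protocol is in dispute. The check sets the text in order and then gives a rough count of the people affected.

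**Reach of a pause of enrolment, by step**

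| Step | Source | Held by a pause of consent? |
|---|---|---|
| New consent | 12.4, 12.4.1 | Yes |
| Screening and kit shipment after consent | 13.1 | Not expressly |
| Randomisation at app sign-up, Week 0 | 12.6, 13.2 | Not expressly |
| First session | Schedule of Procedures | Not expressly |
| Ongoing blinded stimulation | Section 20 is silent | No |
| New open-label active starts | 13.9 against 11.4 and 13.4 | Unclear |

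**People consented but not yet started**

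Inputs: up to 270 randomised (Study Summary); 5 months' enrolment, given as an estimate (11.1); consent and screening in Weeks -3 to -1 (Schedule of Procedures). Assumption: uniform accrual, counting only people who go on to be randomised.

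- 5 months = 5 × 365.25/12 = 152.2 days = 21.7 weeks.
- Rate = 270 / 21.7 = 12.4 per week.
- Waiting = rate × lag. At 1 week: 12.4 × 1 = 12. At 3 weeks: 12.4 × 3 = 37.
- With 1:1 allocation, about half, 6 to 19, would go to active.
- At a 24-day lag: 12.4 × 24/7 = about 43. This is not a maximum, because the 24 days run from the baseline surveys, which follow consent.
- If accrual took 10 months, the rate halves and 6 to 19 people in total would be waiting.

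**After accrual closes**

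Section 11.1 gives the overall timeline: "The study is expected to take approximately 10 months from first participant enrolled to the last open-label visit".

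- 10 months less 5 months of enrolment leaves about 5 months in which a pause of consent has almost nobody to act on.
- If entry to the open-label phase also counts as enrolment, the last such entry falls about 10 weeks after the last randomisation. The period without effect is then about the last 10 weeks.
- At close of accrual, about 12.4 × 10 = 124 people could still be in the blinded phase, half of them (62) on active stimulation, before any attrition.

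**The case against.** The strongest reply is that the lead sentence governs. A study that has stopped does not randomise or start anyone, and the closing sentence does not say that its two steps are the only ones. Section 16.1 is also mandatory, and two suicides or three attempts are hard to see as anything other than grounds to suspect unacceptable risk. Section 16.2 then controls resumption.

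Much of this stands. A reader might infer that the protocol has no means of halting treatment after a trigger. It does have one, in 16.1 together with remote disabling. A reader might also infer from the automatic randomisation in 12.6 that the server would go on allocating people unattended. The documents do not support that: the app link and access code are given out at a Week 0 onboarding session (12.6), which is a video call with study staff (13.2), and only after the investigator has confirmed eligibility (Schedule of Procedures). Nobody starts without a staff action. Nor is enrolment used uniformly throughout: 11.1 uses it for the accrual period, and 13.9 separates consenting from enrolling.

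The gap remains all the same. Section 20 does not define stopping beyond the enrolment pause, and staff act on the sentence that names actions. Section 16.1 requires a separate judgement that section 20 neither makes nor points to, and section 20 does not say whether its pause is lifted under 16.2. A staff-run onboarding call protects participants only if staff know that the hold applies to it.

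**Conclusion.** The point holds as a modest defect in a safety rule. The operative sentence, followed as written, is narrower than the consequence announced above it. It does not hold randomisation or first treatment of people already consented, leaves open-label starts unclear, and has almost no effect once accrual closes.

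The size is roughly 12 to 37 people waiting at a typical moment during accrual, or about half that at 10 months' accrual. These counts rest on uniform accrual and a lag of 1 to 3 weeks, and they are illustrations rather than bounds. They measure how many people the wording leaves uncovered, not how many would in fact be started after a trigger, since 16.1 or the onboarding staff may well intervene. It would go too far to conclude that participants are left without protection or that the two sentences cannot be reconciled. The primary analysis, type I error and power are not affected.

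**What to change.** Keep the lead sentence of section 20, which is the strongest in the section, and replace the closing sentence with:

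> If any stopping rule is reached, new consents, randomisation (issue of app access codes), first treatment and new open-label starts are held at once, the FDA is notified in a supplement, the event is handled as a suspicion of unacceptable risk under section 16.1 (including suspension of ongoing stimulation by remote disabling while the risk is assessed), scheduled safety and Week 10 assessments continue, and the study resumes only under section 16.2.

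This changes one sentence. Its operational costs arise only if a rule is reached: delayed starts for those waiting, delayed open-label treatment, and lost sessions during a suspension.

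The lost sessions can matter. The blinded schedule has 3 × 5 + 7 × 3 = 36 sessions. Losing all of Weeks 1 to 3 leaves 36 − 15 = 21, one below the 22 required by 15.4. Losing two of those weeks leaves 15 − 10 = 5, below the minimum of 10 in 22.3.4. This fix does not alter those session rules or the 24-day start limit. How they apply to a suspension is a separate matter that would need its own worked-out wording.

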21 CLINICAL MONITORING

21.1 SITE MONITORING

The study will be monitored to ensure that it is conducted in conformance with the monitoring plan by an independent CRO to assess continued compliance with the protocol, recognized Good Clinical Practices, FDA's 2013 guidance document "Guidance for Industry Oversight of Clinical Investigations — A Risk-Based Approach to Monitorings, and federal regulations outlined in 21 CFR Part 812

- Subpart A
- Subpart B
- Subpart C -
 - 812.3 Definitions
 - 812.25 Investigational Plan
 - 812.28 Acceptance of data from clinical investigations conducted outside the United States
 - 812.30 FDA action on applications
 - 812.35 Supplemental applications
 - 812.36 Treatment use of an investigational device

CONFIDENTIAL Page **56** of **69**

- 812.40 General responsibilities of sponsors
- 812.43 Selecting investigators and monitors
- 812.46 Monitoring investigations
- 812.47 Emergency research under 50.24 of this chapter
- 812.140 Records
- 812.150 Reports

In addition, the monitor verifies that study records are adequately maintained, that data are reported in a satisfactory manner with respect to timeliness, adequacy, and accuracy, and that the Investigator continues to have sufficient staff and facilities to conduct the study safely and effectively.

The study may also be subject to a quality assurance audit by the Sponsor or its designees, as well as inspection by appropriate regulatory authorities. It is important that the Investigator and relevant study personnel are available during on-site monitoring visits or audits and that sufficient time is devoted to the process.

The organization responsible for monitoring the study is:

Curebase Inc. [name] [name] www.curebase.com

In addition to ensuring adequate communication between the Investigators and the Sponsor, the CRO's duties include on-site visits and review of study documents and reported data. The CRO study representatives will be provided with appropriate device and protocol training prior to the study and will follow a Monitoring Plan for all study-related monitoring activities.

21.2 MONITORING ACTIVITIES

Monitoring visits include a pre-study Site Initiation Visit, periodic Interim Monitoring Visits, and a Close-Out Visit at the end of the site's participation in the study.

Each site's Investigator will allocate adequate time for monitoring activities. The Investigator will also ensure that the monitor or other compliance or quality assurance reviewer is given access to the study-related documents and study-related facilities and has adequate space to conduct the monitoring visit.

Monitoring visits will be documented on monitoring visit reports, and will aim to verify that:

- Compliance with the clinical protocol and applicable regulations is being maintained
- Source data is verified and signed-off upon as accurate

- Participant files are accurate and complete
- Participant withdrawal has been documented (if applicable)
- Participant non-compliance has been documented (if applicable)
- The Investigator and site staff are informed and knowledgeable of all relevant document updates concerning the clinical investigation
- Only authorized individuals are performing study-related functions
- The investigational device is being used according to the protocol and instructions for use
- Adequacy of staffing and facilities
- Signed and dated ICFs have been obtained from each participant
- eCRFs and queries are complete
- All adverse events are reported to the Sponsor
- All serious and unanticipated adverse device events are reported to the Sponsor and the IRB/EC
- All other required IRB/EC reports, notifications, applications, submissions, and correspondence are maintained in the Investigator's files and are accurate
- Corrective and preventive actions have been implemented (if applicable)

21.3 FREQUENCY OF VISITS

To ensure that the study is conducted in accordance with the terms of the clinical protocol, study monitors must visit each investigational site at routine intervals throughout the duration of the study. The exact frequency of visits shall be determined on an individual site basis as detailed in the Clinical Monitoring Plan, and shall depend upon the following factors:

- Rate of participant enrollment
- Experience of the Investigator in conducting clinical studies
- Record of previous site compliance

21.4 AUDIT AND INSPECTIONS

Participation as an Investigator in this study implies acceptance of potential inspection by government regulatory authorities. The Investigator must also be prepared to permit study-related audits and inspections by the Sponsor, CRO, IRB/EC and the site's institutional compliance and quality assurance groups. The Investigator will ensure the capability for inspections of applicable study-related facilities, records, and reports.

22 STATISTICAL ANALYSIS

22.1 STUDY HYPOTHESIS

The primary clinical outcome of the study will be to compare the adjusted mean group differencebased on HDRS-17 scores of the two arms at 10 weeks compared to baseline.

The primary efficacy hypothesis is the change in HDRS-17 scores between 10 weeks and baseline between subjects randomized to the study device relative to those subjects randomized to Sham. The formal statistical hypothesis is as follows:

Ho: $d_{flow} - d_{sham} \le 0$ Ha: $d_{flow} - d_{sham} > 0$

Where d_{flow} and d_{sham} are the adjusted mean group difference in HDRS-17 scores in subjects randomized to Flow and Sham groups, respectively.

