11.5 PRIMARY ENDPOINTS

The primary effectiveness endpoint is the adjusted mean group difference in the HDRS-17 scores at 10 weeks compared to baseline for subjects in the Active device and the Sham device groups.

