11.7 EXPLORATORY ENDPOINTS

- Young Mania Rating Scale (YMRS) at 10 weeks.
- tDCS Adverse Events Questionnaire (AEQ) at 10 and 20 weeks
- Hamilton Anxiety Rating Scale (HAM-A) change at week 10.

- HDRS-17, MADRS, MADRS-s mean decrease, and remission and response rate at 20 weeks (after open-label) compared to open-label start and baseline.
- Correlation between MADRS and MADRS-s.
- Correlation between adherence to stimulation and HDRS-17/MADRS decrease in the active group at 10 weeks.
- Neuropsychological measure: verbal learning (Rey Auditory Verbal Learning Test (RAVLT) and information processing speed (Symbol-Digit Modalities Test (SDMT)
- Treatment acceptability questionnaire (TAQ) as developed by UEL. There is one form at baseline and another at week 10 and 20.
- The within-patient clinically meaningful improvement as defined as at least -3 points on the HDRS-17 scale. The percentage of subjects for each arm that reaches -3 points or more improvement and also the Cumulative Distribution Function Curves of Change in HDRS-17 Score from Baseline to Primary end-point by arm.

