22.5 TESTING OF PRIMARY EFFECTIVENESS HYPOTHESES

The primary effectiveness endpoint is the change in adjusted mean group difference in the HDRS-17 scores between 10 weeks and baseline between subjects randomized to the active study device relative to those subjects randomized to sham. The formal statistical hypothesis is as follows:

$$H_{o}: d_{flow} - d_{sham} \leq 0 \\ H_{a}: d_{flow} - d_{sham} > 0$$

Where d_{flow} and d_{sham} are the adjusted mean group difference in HDRS-17 scores in subjects randomized to Active and Sham groups, respectively.

The mITT population will be the analysis population used to analyze the primary effectiveness endpoint. The endpoint will be analyzed when all randomized subjects have completed their 10-week visit, been withdrawn

from the trial or passed the end of their 10-week follow-up visit window. The difference in the group mean differences will be assessed using a mixed model for repeated measures. If the p-value of the difference in the group mean differences is less than one-sided p= 0.025, then the trial declared a success.

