22.8 SECONDARY EFFECTIVENESS ENDPOINTS

Secondary effectiveness endpoints will be analyzed descriptively.

For continuous variables (CONT), results will be summarized with the numbers of observations, means, standard deviation, median, minimums and maximums. Differences between the two groups, where specified, will be summarized with the differences of the two means, and 95% confidence intervals for the difference between the means. These calculations will be done under the assumption that data for the two groups are independent and approximately normally distributed. The confidence interval for the difference of two means will be calculated under the assumption of unequal variances. If the asymptotic assumptions fail, then nonparametric summary statistics (medians, 25th and 75th percentile) may be displayed as an alternative.

For binary variables (BIN), results will be summarized with patient counts, percentages/rates. Differences between the two groups, where specified, will be summarized with the difference in percent and the Newcombe score 95% confidence interval for the difference of two percentages.

For correlation analysis, Spearman correlation will be used to assess the association between two continuous variables. The correlation coefficient and the 95% confidence intervals will be reported.

CONFIDENTIAL Page **61** of **69**

There are three secondary endpoints controlled multiplicity (see below):

- The mean change in points for MADRS score from baseline to Week 10. This will be evaluated using the same statistical methodology as the primary endpoint.
- Clinical Response will be analyzed as a responder endpoint. Clinical Response is defined as a >50% reduction from the baseline HDRS-17 or MADRS score, MADRS-s at Week 10.
- Remission will be analyzed as a responder endpoint where remission is defined as an HDRS-17 score ≤7 or a MADRS score ≤10). The endpoint will be tested using a two-group large-sample normal approximation test of proportions with a one-sided 0.025 considered significant.
- Quality of life improvement as measured by EQ-5D-3L in the active compared to sham arm at week 10 compared to baseline.

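### Does the one-sided primary hypothesis declare success when active stimulation does worse than sham?

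*Protocol*

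**What the plan says.** Section 22.1 describes the hypothesis this way: "The primary efficacy hypothesis is the change in HDRS-17 scores between 10 weeks and baseline", compared between the two randomized groups. It then prints the alternative "Ha: $d_{flow} - d_{sham} > 0", with the complementary null, and says that the two d terms "are the adjusted mean group difference in HDRS-17 scores in subjects randomized to Flow and Sham groups, respectively". Section 22.5 repeats the same pair of hypotheses and adds the decision rule: "If the p-value of the difference in the group mean differences is less than one-sided p= 0.025, then the trial declared a success".

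The endpoint in section 11.5 is the "adjusted mean group difference in the HDRS-17 scores at 10 weeks compared to baseline". Section 22.8 fixes the direction of the scale, since "remission is defined as an HDRS-17 score ≤7": low scores are good. The only HDRS-17 change that carries a sign is an exploratory item in section 11.7, repeated in 22.9: "The within-patient clinically meaningful improvement as defined as at least -3 points on the HDRS-17 scale". Section 10.2 gives the objective as superiority of active over sham. Section 22.5.1 leaves the details of the mixed model to the SAP, which is not at hand.

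**The concern.** In a one-sided test the direction decides the result. The ordinary reading of a score at 10 weeks compared with baseline is week 10 minus baseline, so improvement is a negative number. The exploratory threshold of -3 points follows that convention. Section 15.2 likewise treats an increase against baseline as worsening. On that convention a device that works gives d_flow - d_sham below zero, while the printed alternative asks for a value above zero. Taken literally, the rule could not declare an effective device successful and would usually pass a harmful one.

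Two things add to the unease. The phrase adjusted mean group difference stands both for the between-arm endpoint (11.5) and for each arm's own d (22.1, 22.5), so the reader cannot recover the sign from the definition. The MADRS change endpoint in 22.8 borrows the primary method, and section 22.10 makes all secondary testing conditional on the primary result, so an error of direction would carry through.

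**Working it through.** **Inputs (section 22.2):** difference 3.2, printed without a sign; SDs 7.1 (active) and 7.9 (sham); one-sided alpha 0.025; 80% power giving 176 subjects; 216 subjects for 87.6% power; 20% attrition giving 270. Allocation is 1:1 (section 22.4), so 216 subjects means 108 per arm.

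**1. Reproduce the plan's figures.**
- Normal approximation: n per arm = (1.960 + 0.842)² × (7.1² + 7.9²) / 3.2² = 7.85 × 112.82 / 10.24 = 86.5, rounded up to 87, or 174 in total.
- Noncentral t with unequal variances: 88 per arm, or 176 in total, gives 80.2% power; 108 per arm gives 87.6%.
- Attrition: 216 / 0.80 = 270.

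All the stated figures are recovered. They depend on the size of the difference and not on its sign, so they do not settle the direction.

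**2. What the literal rule does under each definition of d, for a true 3.2-point benefit.**
- Standard error at 108 per arm = √(7.1²/108 + 7.9²/108) = √(112.82/108) = 1.022, so |z| = 3.2 / 1.022 = 3.13.
- If d is baseline minus week 10, the contrast is +3.2. The chance of success is Φ(3.13 - 1.96) = 0.879 by the normal approximation and 0.876 by the t distribution. This is the plan's own power.
- If d is week 10 minus baseline, the contrast is -3.2. The chance of success is Φ(-3.13 - 1.96), about 2 × 10⁻⁷. By symmetry, a 3.2-point harm would pass with probability about 88%.

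**3. Which definition does the protocol use?**

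| Points to week 10 minus baseline | Points to a reduction |
|---|---|
| Endpoint worded as week 10 compared with baseline (11.5) | Outcomes described as a mean decrease in HDRS-17 and MADRS (11.7, 22.9) |
| Improvement of -3 points (11.7, 22.9) | Response defined as a reduction from baseline of more than 50% (22.8) |
| Increase against baseline counted as failure (15.2) | Planning difference written as positive 3.2 (22.2), beside an alternative above zero |

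Section 22.1 itself speaks only of "the change in HDRS-17 scores between 10 weeks and baseline", which fixes no order of subtraction. Neither column is decisive. The -3 item is a within-patient exploratory threshold that does not refer to d, and the 3.2 may simply be an absolute value.

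**4. What does not depend on the definition.** If d is week 10 minus baseline with the inequalities reversed, or baseline minus week 10 with them kept, the test is the same. Power for a 3.2-point benefit is 87.6% at 216 subjects in both cases. An observed 3.2-point benefit with that standard error gives one-sided p of about 0.001 in the direction of benefit and about 0.999 against it.

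**The case for a change.** The strongest case for a change is that the hypothesis is not left to the SAP. The protocol prints it twice and attaches the success rule. A SAP that models change from baseline in the usual way would then disagree with the printed inequality. The trial is meant to support a premarket approval application (section 24.4), a setting in which the confirmatory hypothesis should be readable without inference. One defining sentence would remove the doubt at almost no cost.

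All of that stands as a comment on drafting. The sign of d is not stated, the exploratory item uses a notation that clashes with the printed inequality if d is read in the same way, and one phrase serves for two quantities. What does not stand is the step from an undefined sign to a reversed test. That step needs d to be week 10 minus baseline, which the protocol does not say. It also needs an analyst to apply the inequality mechanically against a superiority objective stated without ambiguity in section 10.2. An arm-by-arm table of HDRS-17 means would expose such a slip at once.

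**Conclusion.** The hypothesis is under-defined and has not been shown to be reversed. It is correct as printed if d is the mean reduction in HDRS-17, a reading the protocol supports in several places. The figures of 2 × 10⁻⁷ and 88% are arithmetically right, but they hold only if d is week 10 minus baseline and the inequality is nevertheless applied literally. They are not realistic operating characteristics of this trial.

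This is a gap that analysts fill sensibly. The objective fixes the direction of benefit, the contrast to be programmed belongs with the model details that section 22.5.1 leaves to the SAP, and both consistent definitions give the same test, the same p-value and the same 87.6% power. The sample sizes of 176, 216 and 270 are unaffected. Writing down the order of subtraction would be tidy if the text were reopened for another reason, but no result turns on it. The conclusion assumes that the SAP, which was not available, sets the contrast in the direction of benefit.
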